## 18. Provisions to Monitor the Data to Ensure the Safety of Participants

### 18.1. Data Integrity Monitoring.

*The sponsor-investigator will permit direct access to the study monitors and appropriate regulatory authorities to the study data and to the corresponding source data and documents to verify the accuracy of these data.*

## MEDICAL PROTOCOL (HRP-590)

PROTOCOL TITLE: Combining cerebellar tDCS and constraint-induced language therapy in non-fluent aphasia: a novel approach to target discourse

VERSION DATE: 08/09/2023

*Independent monitoring of the clinical study for clinical protocol compliance will be conducted by University of Minnesota's Clinical and Translational Science Institute (CTSI) clinical trial monitoring service.*

*The CTSI monitors will confirm that study activities are in compliance with the approved protocol and applicable regulatory authorities (FDA, IRB, local and State regulations).*

*Frequency of monitoring visits will occur:*

- *After IRB approval*
- *As soon as possible after the first subject is enrolled*
- *During the study data collection phase*
- *After the last subject has completed his/her participation in the study*

*This monitoring schedule may be revised based on the following considerations:*

- *Accrual rate*
- *Protocol deviations or non-compliance with regulatory authorities*
- *Magnitude of data corrections required*
- *Study stage (e.g. start-up or follow-up)*
- *Complexity of the trial*
- *Request (IRB, Investigator, other etc.)*
- *DSMB recommendation*

*Monitoring visits will be performed annually, at a minimum. The sponsor-investigator will permit direct access to the study monitors and appropriate regulatory authorities to the study data and to the corresponding source data and documents to verify the accuracy of these data.*

*Primary responsibilities of the monitors will include verifying the following:*

- *Investigator qualifications*
- *Facilities and equipment*
- *Storage, dispensing and disposition of investigational products*
- *Protocol compliance*
- *Informed consent*
- *Training and delegation of authority*
- *Subject eligibility*
- *Recruitment, screening and enrollment*

## MEDICAL PROTOCOL (HRP-590)

PROTOCOL TITLE: Combining cerebellar tDCS and constraint-induced language therapy in non-fluent aphasia: a novel approach to target discourse

VERSION DATE: 08/09/2023

- *Verification of data and data clarification*
- *Adverse event reporting*
- *FDA correspondence*
- *Deviations*

### 18.2. Data Safety Monitoring

**Adverse Event (AE) vs. Serious Adverse Event (SAE):** An adverse event is any undesirable experience associated with the use of a medical product in a participant. A serious adverse event (SAE) should immediately be reported to the FDA when the participant outcome is:

- **Death:** Report if you suspect that the death was an outcome of the adverse event, and include the date if known.
- **Life-threatening:** Report if suspected that the patient was at substantial risk of dying at the time of the adverse event, or use or continued use of the device or other medical product might have resulted in the death of the patient.
- **Hospitalization (initial or prolonged):** Report if admission to the hospital or prolongation of hospitalization was a result of the adverse event. Emergency room visits that do not result in admission to the hospital should be evaluated for one of the other serious outcomes (e.g., life-threatening; required intervention to prevent permanent impairment or damage; other serious medically important event).
- **Disability or Permanent Damage:** Report if the adverse event resulted in a substantial disruption of a person's ability to conduct normal life functions, i.e., the adverse event resulted in a significant, persistent or permanent change, impairment, damage or disruption in the patient's body function/structure, physical activities and/or quality of life.
- **Congenital Anomaly/Birth Defect:** Report if you suspect that exposure to a medical product prior to conception or during pregnancy may have resulted in an adverse outcome in the child.
- **Required Intervention to Prevent Permanent Impairment or Damage (Devices):** Report if you believe that medical or surgical intervention was necessary to preclude permanent impairment of a body function, or prevent permanent damage to a body structure, either situation suspected to be due to the use of a medical product.
- **Other Serious (Important Medical Events):** Report when the event does not fit the other outcomes, but the event may jeopardize the patient and may require medical or surgical intervention (treatment) to prevent one of the other outcomes. Examples include allergic bronchospasm (a serious problem with

## MEDICAL PROTOCOL (HRP-590)

PROTOCOL TITLE: Combining cerebellar tDCS and constraint-induced language therapy in non-fluent aphasia: a novel approach to target discourse

VERSION DATE: 08/09/2023

breathing) requiring treatment in an emergency room, serious blood dyscrasias (blood disorders) or seizures/convulsions that do not result in hospitalization.

The development of drug dependence or drug abuse would also be examples of important medical events.

**Severity of an adverse event:** The following guidelines will be used to describe severity of an adverse event.

- **Mild:** Events require minimal or no treatment and do not interfere with the participant's daily activities.
- **Moderate:** Events result in a low level of inconvenience or concern with the therapeutic measures. Moderate events may cause some interference with functioning.
- **Severe:** Events interrupt a participant's usual daily activity and may require systemic drug therapy or other treatment. Severe events are usually potentially life-threatening or incapacitating. Of note, the term "severe" does not necessarily equate to "serious".

**Relationship to study intervention:** The following guidelines will be used to describe the "relatedness" of an adverse event.

- **Definitely Related:** There is clear evidence to suggest a causal relationship, and other possible contributing factors can be ruled out. The clinical event, including an abnormal laboratory test result, occurs in a plausible time relationship to study intervention administration and cannot be explained by concurrent disease or other drugs or chemicals. The response to withdrawal of the study intervention (dechallenge) should be clinically plausible. The event must be pharmacologically or phenomenologically definitive, with use of a satisfactory rechallenge procedure if necessary.
- **Probably Related:** There is evidence to suggest a causal relationship, and the influence of other factors is unlikely. The clinical event, including an abnormal laboratory test result, occurs within a reasonable time after administration of the study intervention, is unlikely to be attributed to concurrent disease or other drugs or chemicals, and follows a clinically reasonable response on withdrawal (dechallenge). Rechallenge information is not required to fulfill this definition.
- **Potentially Related:** There is some evidence to suggest a causal relationship (e.g., the event occurred within a reasonable time after administration of the trial medication). However, other factors may have contributed to the event (e.g., the participant's clinical condition, other concomitant events). Although an AE may rate as "potentially related" soon after discovery, it can be flagged as requiring

## MEDICAL PROTOCOL (HRP-590)

PROTOCOL TITLE: Combining cerebellar tDCS and constraint-induced language therapy in non-fluent aphasia: a novel approach to target discourse

VERSION DATE: 08/09/2023

more information and later be upgraded to “probably related” or “definitely related”, as appropriate.

- **Unlikely to be related:** A clinical event, including an abnormal laboratory test result, whose temporal relationship to study intervention administration makes a causal relationship improbable (e.g., the event did not occur within a reasonable time after administration of the study intervention) and in which other drugs or chemicals or underlying disease provides plausible explanations (e.g., the participant’s clinical condition, other concomitant treatments).
- **Not Related:** The AE is completely independent of study intervention administration, and/or evidence exists that the event is definitely related to another etiology. There must be an alternative, definitive etiology documented by the clinician.

**Expectedness:** The Investigator will be responsible for determining whether an adverse event is expected or unexpected. An adverse event will be considered unexpected if the nature, severity, or frequency of the event is not consistent with the risk information previously described for the study intervention.

**Reporting of adverse events:** Information on all adverse events will be collected including the:

- Event description
- Time of onset
- Assessment of severity
- Relationship to study intervention
- expectedness
- Time of resolution/stabilization of the event

All adverse events occurring while on study will be documented appropriately regardless of relationship. All adverse events will be followed to adequate resolution.

Any medical condition that is present at the time that the participant is screened will be considered as baseline and not reported as an adverse event. However, if the participant’s condition deteriorates at any time during the study, it will be recorded as an adverse event.

The investigator will record all reportable events with start dates occurring any time after informed consent is obtained until 7 (for non-serious adverse events) or 30 days (for serious adverse events) after the last day of study participation. At each study visit,

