## MEDICAL PROTOCOL (HRP-590)

PROTOCOL TITLE: Combining cerebellar tDCS and constraint-induced language therapy in non-fluent aphasia: a novel approach to target discourse

VERSION DATE: 08/09/2023

*of 21.5 hours of participation over the course of the study. If a participant misses an intervention session, we will attempt to make it up during that same week of intervention and reschedule the assessment day. The timing of the assessment day post intervention is critical as tDCS does not appear to have long-lasting effects. The post intervention assessment visit would have to take place within 1-2 days of the last intervention day. If rescheduling is not an option, the total number of intervention sessions attended will be noted in the data. However, if 2 sessions have been missed within either of the intervention periods, the participant will need to be re-enrolled or dropped from the study. Participants will be randomly assigned to receive either the real or sham tDCS first.*

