### Schedule of Events

Table 1. Schedule of Research Activities.

	Screen / Baselin		Interventio n A or B	Follow- Up 1	Washout	Baselin e 2	Interventio n A or B	Follow- Up 2
Day/Week	Visit 1	Visit 2 Anytime after consent	Visits 3-8 6 total sessions: 3 sessions per week across 2 weeks). Must occur	Visit 9 must occur within 1 day of visit 8	4 weeks	Visit 10 can occur anytime after the 4 week washo ut	Visits 11-16 6 total sessions: 3 sessions per week across 2 weeks Must occur within 5	Visit 17 must occur within 1 day of visit 16
Screen for Eligibility	x							
Consenting Process	x							
Western Aphasia Battery	If needed							

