## 12. Withdrawal of Participants

### 12.1. Withdrawal Circumstances:

*Participants are free to withdraw from participation in the study at any time upon request. An investigator may discontinue or withdraw a participant from the study for the following reasons:*

- *Pregnancy*
- *Significant study non-compliance*
- *If any clinical adverse event (AE) or other medical condition or situation occurs such that continued participation in the study would not be in the best interest of the participant*
- *If the participant meets an exclusion criterion (either newly developed or not previously recognized) that precludes further study participation*

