### 12.2. Withdrawal Procedures:

*If a participant wishes to withdraw or we determine that the participant should withdraw, we will terminate data collection and discuss with the participant the reasons for withdrawal. All data collected up to that point will be used in analysis unless the participant wishes for their data not to be used.*

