## MEDICAL PROTOCOL (HRP-590)

PROTOCOL TITLE: Combining cerebellar tDCS and constraint-induced language therapy in non-fluent aphasia: a novel approach to target discourse

VERSION DATE: 08/09/2023

the investigator will inquire about the occurrence of the adverse event since the last visit.

**The following are considered “Promptly Reportable Events” by the UMN IRB and will be reported as “Reportable New Information” within 5 business days of learning of the event:**

- Unexpected Death: Unexpected death of a locally enrolled participant/subject who has not withdrawn from the research whether the death is considered related to the research or not. Death is considered unexpected if the risk of death is not listed in the consent form or is not listed as a possible event in protocol-related documents such as the IRB approved protocol or the Investigator’s Brochure.
- Risk: Information that indicates a new or increased risk, or a safety issue.
- New information (e.g., an interim analysis, safety monitoring report, publication in the literature, sponsor summary report, or investigator finding) indicates an increase in the frequency or magnitude of a previously known risk, or uncovers a new risk. Do not submit Investigational New Drug (IND) safety letters, Medwatch reports, or other such individual reports to the IRB unless, in the opinion of the investigator, the event or information in the report constitutes a UPIRTSO or the report requires a change to the protocol and/or the consent form.
- An adverse event that indicates a potential increase in risk or reduction in benefit (such as those that may prompt a change to the protocol or consent form).
- An investigator brochure, package insert, or device labeling is revised to indicate an increase in the frequency or magnitude of a previously known risk, or to describe a new risk.
- Withdrawal, restriction, or modification of a marketed approval of a drug, device, or biologic used in a research protocol.
- Protocol violation that harmed subjects or others or that indicates participants/subjects or others might be at increased risk of harm.
- Complaint of a participant/subject that indicates participants/subjects or others might be at increased risk of harm or at risk of a new harm.
- Any changes significantly affecting the conduct of the research outside of the investigator’s control or not directed by the investigator, e.g., a new therapy for the condition under study is proving highly effective.

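### No scheduled contact after Visit 17 covers the 7-day and 30-day adverse event windows in 18.2, and for withdrawals 12.2 conflicts with 18.2 and 3.2

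*Combined protocol and SAP*

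**What the plan says.** Section 18.2 makes three commitments. Reportable events are recorded from consent "until 7 (for non-serious adverse events) or 30 days (for serious adverse events) after the last day of study participation". At each study visit "the investigator will inquire about the occurrence of the adverse event since the last visit". And "All adverse events will be followed to adequate resolution". It gives no schedule or method for contact between visits or after the last one.

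Table 1 in 5.2 ends with the second follow-up assessment: "Visit 17 must occur within 1 day of visit 16". The text of 5.2 allows slightly longer: "The post intervention assessment visit would have to take place within 1-2 days of the last intervention day". Section 5.3 gives 17 visits in total.

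On withdrawal, 12.1 lists as one ground "If any clinical adverse event (AE) or other medical condition or situation occurs" that makes continuing contrary to the participant's interest. Section 12.2 then says that on withdrawal "we will terminate data collection and discuss with the participant the reasons for withdrawal". Section 3.2, item 4, says the team will approach participants who drop out and ask them to complete the adverse events survey, but sets no date.

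Section 11.1 adds daily check-ins during the intervention phases and staff contact details in a welcome packet.

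**The concern.** The plan commits itself to a period of safety observation after participation ends, yet it schedules no occasion on which anyone asks. An absence of late events could then mean only that nobody enquired.

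The people concerned are poorly placed to volunteer a report. Section 2.1 describes the condition as one of limited verbal output, and 5.2 plans help with reading and interpreting the quality-of-life questionnaire. The 30-day window is not a formality either: 13.1 notes that people after stroke are more prone to seizures, and 18.2 gives seizures without hospital admission as an example of a serious event.

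Section 15.3 reports adverse events as counts and rates, and these depend on how long and how actively each participant was observed. The pilot is meant to inform a larger trial, so a safety record with an unrecognised gap would be carried forward. Someone withdrawn because of an event is the person whose outcome matters most, and 12.2 as written ends collection for that person.

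**Working it through.** **1. Visit count.** Adding up Table 1: screening and consent 1, baseline 1, first intervention 6, first follow-up 1, second baseline 1, second intervention 6, second follow-up 1.
1 + 1 + 6 + 1 + 1 + 6 + 1 = 17, which agrees with 5.3. Duration is 2 + 4 + 2 = 8 weeks, in line with the stated 2 months. No visit is left over for safety follow-up. (Section 4.1 gives 12 sessions over 4 weeks per condition, where Table 1 and 5.3 give 6 over 2 weeks. Those passages must be reconciled, but either way nothing follows the final assessment.)

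**2. Coverage of the windows for completers.** Assume Visit 17 is the last day of participation, and count days from the last stimulation.

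| | Table 1 timing | 5.2 text timing |
|---|---|---|
| Last scheduled enquiry (Visit 17) | day 1 | day 2 at most |
| End of non-serious window | 1 + 7 = day 8 | 2 + 7 = day 9 |
| End of serious window | 1 + 30 = day 31 | 2 + 30 = day 32 |
| Scheduled contacts after Visit 17 | 0 | 0 |
| Window days covered | 0 of 7; 0 of 30 | 0 of 7; 0 of 30 |

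The difference between Table 1 and the text of 5.2 needs reconciling but does not change the result.

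**3. Enquiry after real stimulation, by sequence.** This step assumes that the visit-based enquiry in 18.2 applies at Visit 10.
- Real first: Visit 10 follows the 4-week washout and looks back to Visit 9, so enquiry extends at least 4 × 7 = 28 days after the last real session.
- Real second: the last enquiry is Visit 17, 1-2 days after the last real session.

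The Adverse Events row of Table 1 shows no clear mark at the second baseline, and its columns are broken in the text available. The first bullet therefore rests on the wording of 18.2, not on the table.

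**4. Withdrawals, side by side.**
- 18.2: events are recorded through the windows, and all are followed to resolution.
- 12.2: data collection ends at withdrawal, with a discussion of the reasons.
- 3.2, item 4: dropouts are approached for the adverse events survey, with no date or look-back period.

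Read literally, 12.2 rules out what the other two require. The 3.2 outreach is a real contact, but without a date it cannot be shown to cover either window.

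**5. Size of the remedy.** 5 participants enrolled (10.1) × 2 contacts = 10 contacts at most.

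**The case against.** The strongest reply is that 18.2 is a recording rule based on when an event starts, and does not restrict the source to active enquiry. Participants hold staff contact details, so an unprompted report inside the window would be recorded. That stands. A reader might infer that late events cannot be captured at all, and the documents do not support this: what is missing is scheduled contact. The daily check-ins in 11.1 do not fill the gap, because they are confined to the intervention phases and are not described as adverse event enquiry.

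A reader might also infer that withdrawn participants receive no safety contact. Section 3.2 plans outreach to them, and 12.2 itself includes a discussion of reasons. It can be argued further that the specific follow-to-resolution rule in 18.2 overrides the general stop in 12.2. That reading is possible, but the protocol does not state it, and staff following 12.2 would stop.

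Counting from the last stimulation would give 7 − 1 = 6 and 30 − 1 = 29 uncovered days. Section 18.2 starts its windows after the last day of participation, so that is the wrong origin.

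Nor is it right that delayed events after real stimulation are captured in only one sequence. Unprompted reports remain possible in both, and the Visit 10 enquiry is itself uncertain from Table 1. The shorter enquiry attaches to whichever condition comes second, so it is not in itself a bias between real and sham, although 5 participants cannot be split equally between sequences.

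On importance, the tolerance aim in 1.1 is measured by the adverse events questionnaire, given after each intervention phase. It does not depend on the windows. The protocol also expects mostly local sensations under the electrode and short-lived effects of stimulation. These points limit the stakes, but they do not explain how a window the protocol itself sets is to be observed. The consent pages and standard operating procedures were not available and may describe a reporting route. Table 1 and 18.2 should still agree with it.

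**Conclusion.** The point holds in a limited form. For completers, scheduled contact covers none of the 7-day window and none of the 30-day window, and ascertainment of late events is left to unprompted reports from people with impaired expressive language. This assumes that Visit 17 is the last day of participation, a term the protocol does not define for completers or withdrawals.

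The difference between sequences, at least 4 weeks against 1-2 days of active enquiry after real stimulation, is conditional on enquiry taking place at Visit 10. For withdrawals, 12.2 conflicts with 18.2 and with 3.2, and the three must be reconciled.

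The efficacy analysis and the questionnaire-based tolerance aim are unaffected. What is affected is the completeness of the adverse event counts and rates. The correction should be made because the plan, followed as written, does not actively observe its own safety windows, and putting that right costs little.

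**What to change.** - Add to Table 1 and 18.2 two brief adverse event contacts, timed to the ends of the 7-day and 30-day windows after Visit 17, or after the last session attended for those who withdraw. Use a method the participant has agreed to; 16.5 requires signed consent for text messages and unsecured email.
- Define the last day of participation for completers and for withdrawals.
- Align the Adverse Events row of Table 1 with the visit-based enquiry in 18.2, in particular at the second baseline, and reconcile the timing of Visit 17 between Table 1 and the text of 5.2.
- Reconcile 12.2 with 3.2 and 18.2, so that withdrawal ends sessions and efficacy assessments while adverse event collection continues unless the participant declines. Give the dropout survey a date and a look-back period.

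The contact at the end of the 30-day window would bring serious-event enquiry after a second-period condition to about 1 + 30 = 31 days from the last session, comparable with the 28 days or more after a first-period condition. Non-serious events would still be sought for longer after the first period, so the report should state the observation time behind each count.

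The cost is protocol wording, at most 10 short contacts, communication support for some of them, and a mention in the consent form. It needs no new staff or visits. One contact at the end of the 30-day window would be cheaper, but recall of minor events from the first week would be weaker.
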